< 7.5 & ≥ 5	2 – 4	1 - 2.5
< 5 & ≥ 2.5	2 - 4	1.5 - 2.5
< 2.5 & ≥ 1	2 – 4	1
0		

NOTE: When beginning Phase I (6-12 months), hold patient at 7.5 mg/day, for at least one week.

Directions for Rescue Taper

Reactivations can be mild or severe. Mild reactivations are considered an increase in inflammation up to the 1+ level in anterior chamber cell or vitreous haze. Severe reactivations are considered an increase in inflammation up to the 2+ level or higher in anterior chamber cell or vitreous haze. Retinal/choroidal lesions may be considered mild or severe at the discretion of the study physician.

If uveitis reactivates:

- Increase oral prednisone up to a dose of 1 mg/kg for severe reactivations, or for mild reactivations, up to double the dose at which the flare occurred, until uveitis is controlled. Then re-taper according to the guidelines.

Uveitis is considered non-responsive if inflammation does not increase but does not further improve after the first 4 weeks of treatment on 1mg/kg oral prednisone.

If uveitis is non-responsive:

- Hold the current dose of prednisone for an additional week. If still no improvement, treatment failure due to futility may be declared, and patients may proceed to Phase II. Alternatively, other therapies may be added, but these should be noted as a protocol deviation.
- If treatment failure is declared due to futility in Phase I, before the primary endpoint of 6 months, patients may switch to Phase II. Patients who refuse to switch to Phase II should be encouraged to return for a 6-month visit. Patients who switch to Phase II will already be followed.
- If treatment failure is declared due to futility in Phase II, before the primary endpoint of 6 months, patients will be treated according to best medical judgment. If treatment failure is declared prior to 6 months, Phase I and Phase II, every attempt must be made to bring patients back for their 6 month assessment.

After suppression of uveitis is once again achieved (either in the case of reactivation or non-response) follow the taper guidelines for Phase I. Patients who have failed the treatment to which they are randomized will then switch treatments, begin Phase II, and follow the same taper guidelines as Phase I (0-6 months). If patients flare during Phase II, they can follow directions for the rescue taper listed above. Patients who fail the second treatment at the 6 month endpoint will be treated as per the investigators discretion.

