17. Additional exploratory modeling will be conducted using clustered multinomial logistic regression using all time points and all observations of anterior chamber cells, vitreous haze, and retinal/choroidal lesions.

3.2.3 Specific Aim 2

Primary Analysis.

The primary analysis will compare the proportion of successes between (a) patients treated with mycophenolate mofetil following failure on methotrexate and (b) patients treated with methotrexate following failure on mycophenolate mofetil.

Specifically, we will conduct a logistic regression in which success or failure will be the outcome, and the predictors (regressors, independent variables) will be treatment group and reason for failure of the first drug (lack of efficacy vs any other reason). Supplementary analyses will include anatomic location (intermediate vs posterior/pan) and country. We will test the hypothesis that the coefficient for treatment group equals zero (i.e., that mycophenolate mofetil rescue after methotrexate failure has the same result as methotrexate rescue after mycophenolate mofetil failure). All alpha levels will be two-sided.

It is important to emphasize that estimation of the success rate of the second drug following the failure of the first is a central goal of the trial, arguably as or more important than the hypothesis test itself. The success rates and confidence intervals will be presented regardless of the results of the hypothesis test.

Secondary Analyses.

The following secondary analyses are planned.

We will also present the estimated success proportion in both treatment groups, together with the 95% confidence intervals. The two groups are the individuals who were undergoing methotrexate rescue therapy after mycophenolate mofetil, and those who were undergoing mycophenolate mofetil rescue therapy after methotrexate. Logistic regression will also be used to adjust for study site.

The second prespecified analysis will compare the rate of success between rescue patients and first-line patients, using logistic regression; we will test the hypothesis that the coefficient for rescue/initial equals zero. A supplemental variation of this analysis will include an additional predictor for whether the patient was on rescue therapy due to lack of efficacy, lack of safety or intolerance, or anatomic location. Two separate analyses are planned, each with an alpha of 0.05.

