Thus, the number of available patients for Specific Aim 2 are highly dependent on the results from Specific Aim 1. Scientifically, the result of rescue therapy is important regardless of the result in Aim 1. More power will be available for the primary comparison in Specific Aim 2 if treatment in Specific Aim 1 yielded relatively high and similar failure rates for both drugs. However, even if success rates are very different in Aim 1, the descriptive analyses will still provide important information to guide decision-making on second-line treatment.

Here, $N_0=108$, and r_1 is assumed to be 0.9 (10% loss to follow-up). For planning Specific Aim 2, we assume a success rate of 60% for patients treated with drug A Specific Aim 1, and a success rate of 40% for those treated with drug B. This is a conservative estimate of the difference expected based on retrospective studies^{12, 18-20} and consistent with the pilot study. Finally, we are assuming an additional 5% loss to follow-up during Specific Aim 2 (in addition to the 10% already lost), so that $r_2=0.95$. The results are summarized in the following table, where the number enrolling does not include loss to follow-up, and the “expected complete” column has taken loss to follow-up into account (n_{jk}).

We anticipate the following:

Initial/Second Treatment	Expected Enrollment SA/2	Expected to Complete SA/2
B/A	58.3	55.4
A/B	38.9	36.9

Thus, we expect a total of $n_1=58$ patients (rounding down) to have failed one first-line therapy to be enrolled in rescue therapy. Similarly, we expect $n_0=38$ patients to be enrolled in the other rescue regimen.

Previous observational studies suggest a 42% success rate of mycophenolate mofetil in methotrexate-failing patients.²⁴ A simple power analysis for comparing these proportions may be found from the formula (see Chao et al, p. 87):¹⁵

$$1 - \beta = \Phi \left(\frac{|p_1 - p_0|}{\sqrt{\frac{p_0(1-p_0)}{n_0} + \frac{p_1(1-p_1)}{n_1}}} - z_{\alpha/2} \right)$$

where p_0 is the probability of success with methotrexate rescue following mycophenolate mofetil failure, p_1 the probability of success with mycophenolate mofetil rescue following methotrexate failure, and Φ is the cumulative distribution function of the standard normal distribution. These assumptions yield a power of 0.87 if the rate of success with methotrexate rescue is 0.15. We have approximately 80% power to detect a difference of 17% if the probability of success with mycophenolate mofetil is 0.42.

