A power table for sensitivity analysis is provided. We chose selected scenarios of potential interest to show the wide range of scenarios for which we have sufficient power. The main scenario is the first row of the table; in other rows, we varied the number of patients or the success fractions for the first drug used. In particular, the results are not sensitive to the efficacy difference found in Specific Aim 1.

Power Table for Specific Aim 2

Drug A, then Drug B (number)	Drug B, then Drug A (number)	Success probability of Drug B in patients failing Drug A	Success probability of Drug A in patients failing Drug B	Approximate Power
58	38	0.42	0.15	87%
58	38	0.42	0.17	80%
58	38	0.15	0.42	83%
58	76	0.42	0.15	94%
116	38	0.42	0.15	96%
40	40	0.42	0.15	80%
58	38	0.40	0.15	80%

To summarize, the anticipated number of patients from Specific Aim 1 (58 enrolled in Drug A, and 38 in Drug B) should provide approximately 80% power to detect a difference of 25% between the two groups, assuming a success probability of 42% and a two-tailed alpha of 0.05.

Secondary Outcomes in Specific Aim 2.

1. Confidence intervals for the probability of success will be reported for each rescue group and anatomic location (i.e. Patients receiving methotrexate or mycophenolate mofetil as first treatment versus receiving it as their second, rescue treatment). Note that in the event that there are insufficient numbers of patients available in one arm of Specific Aim 2 (for instance, far fewer patients available for methotrexate rescue than we anticipate), confidence intervals for estimating the proportion of success can still be computed for the anatomic locations in the other arm.
2. We propose, for each rescue group, to conduct logistic regression using success as an outcome, and reason for failure of the first drug as a categorical covariate (safety, efficacy, tolerability). An overall likelihood ratio test for each will be conducted, with an alpha of $0.05/2=0.025$.
3. An additional comparison will be undertaken between first-line and rescue patients with both methotrexate and mycophenolate mofetil.
4. Additionally, the same secondary outcomes assessed in Aim 1 will be analyzed using similar methods.

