3.7 Multiple comparisons

An alpha of 0.05 will be used for the primary analysis of Specific Aims 1 and the primary analysis of Specific Aim 2. The prespecified subgroup analyses of Specific Aim 1 will be conducted at an alpha level of 0.05 (as stated above) as well. However, the use of an overall test prior to subgroup analysis protects the overall type I error rate for the primary outcome, a procedure we apply within the analysis of each secondary outcome as well.

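### The Aim 2 power text claims about 80% power for a 17-point difference; the SAP's own formula gives about 43%, and 0.17 is the comparator's success rate, not the difference.

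*Combined protocol and SAP*

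**What the plan says.** SAP 3.4.2, under Specific Aim 2, expects 58 patients in one rescue group and 38 in the other. It takes 0.42 as the success rate for mycophenolate after methotrexate failure and prints a normal-approximation power formula. Two results follow. The first is "These assumptions yield a power of 0.87 if the rate of success with methotrexate rescue is 0.15". The second, in the next sentence, is "We have approximately 80% power to detect a difference of 17% if the probability of success with mycophenolate mofetil is 0.42".

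A power table comes next. Its second row has 58 and 38 patients, 0.42 and 0.17, and 80% power. The column holding 0.17 is headed "Success probability of Drug A in patients failing Drug B", so the entry is a rate. The section closes by saying that the expected numbers "should provide approximately 80% power to detect a difference of 25% between the two groups", for the same 42% success probability and two-tailed alpha 0.05.

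On the standing of the comparison, SAP 3.2.3 says: "The primary analysis will compare the proportion of successes between (a) patients treated with mycophenolate mofetil following failure on methotrexate" and the reverse sequence. SAP 3.7 adds: "An alpha of 0.05 will be used for the primary analysis of Specific Aims 1 and the primary analysis of Specific Aim 2".

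**The concern.** The section gives two detectable differences, 17 and 25 points, for the same group sizes, reference rate, alpha and power. They cannot both be right. The 17-point figure also sits badly with the sentence before it: 0.42 versus 0.15 is a 27-point gap with 87% power, and narrowing the gap to 17 points could not cost only seven points of power. The likely explanation is that the comparator's success rate was written where the difference belonged.

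What is at stake is how a non-significant Aim 2 test would be read. At 80% power for 17 points, a null result would be fair evidence against a difference that large between rescue sequences. At 43%, the test would miss such a difference more often than not (100% − 43% = 57%).

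**Working it through.** **Inputs (SAP 3.4.2, Specific Aim 2).** Mycophenolate rescue: n1 = 58, p1 = 0.42. Methotrexate rescue: n0 = 38, p0 varied. Two-sided alpha 0.05, z = 1.96.

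**Formula (as printed in the SAP).** Power = Φ( |p1 − p0| / √[p0(1 − p0)/n0 + p1(1 − p1)/n1] − 1.96 ). The mycophenolate variance term is always 0.42 × 0.58 / 58 = 0.004200.

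**Step 1: reproduce the plan's 0.87 (p0 = 0.15).**
- 0.15 × 0.85 / 38 = 0.003355; sum 0.007555; square root 0.08692.
- 0.27 / 0.08692 = 3.106; minus 1.96 = 1.146; Φ = 0.874. This agrees with the stated 0.87.

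Applied to all seven table rows in order, the formula gives 87.4, 80.2, 82.9, 94.1, 95.5, 80.0 and 82.3%, against printed values of 87, 80, 83, 94, 96, 80 and 80%. The first six agree to rounding, so this is evidently the formula that was used. The last row is about two points off and plays no part in this finding.

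**Step 2: the disputed sentence, a true 17-point difference (p0 = 0.25).**
- 0.25 × 0.75 / 38 = 0.004934; sum 0.009134; square root 0.09557.
- 0.17 / 0.09557 = 1.779; minus 1.96 = −0.181; Φ = 0.428.

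Power is 42.8%, not 80%.

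**Step 3: read 0.17 as the comparator rate (p0 = 0.17, difference 0.25).**
- 0.17 × 0.83 / 38 = 0.003713; sum 0.007913; square root 0.08896.
- 0.25 / 0.08896 = 2.810; minus 1.96 = 0.850; Φ = 0.802.

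This matches the stated 80%. Solving for exactly 80% power gives p0 = 0.171, a detectable difference of 0.42 − 0.171 = 0.249.

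**Step 4: can any other reading rescue 80% for 17 points?**

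| Variant, 17-point difference | Power |
|---|---|
| Comparator higher (0.42 vs 0.59) | 38.0% |
| Pooled variance | 39.5% |
| Group sizes swapped | 41.0% |
| Expected completers, 55.4 and 36.9 | 41.5% |
| Unrounded enrollment, 58.3 and 38.9 | 43.3% |
| One-sided alpha 0.05 | 55.3% |
| One-sided alpha 0.05, unrounded enrollment | 55.9% |
| Exact chi-square | 39.9% |
| Fisher's exact test | 35.2% |

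Except in the first row, the rates are 0.42 and 0.25. None comes near 80%. At the same allocation, 80% power for 0.42 versus 0.25 would need about 145 and 95 patients, 240 in all against 96 planned, or 2.5 times as many.

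**Labels.** The text expects 58.3 patients in the B-then-A sequence, while the table puts 58 under A-then-B. Rows are therefore matched here by group size and rate (58 patients at 0.42). The text surrounding the formula names the drugs, so no result depends on the letters.

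**The case against.** The strongest reply is that this is a slip of wording that the SAP itself resolves. The table and the closing summary are right, the preceding sentence shows that success rates are being varied, and neither the sample size, alpha nor any decision rule depends on the sentence. All of that stands, and it limits the finding to a correction of text.

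A second reply concerns importance. SAP 3.4.2 presents Aim 2 mainly as estimation of each rescue success rate with confidence intervals and treats the between-group test as one analysis among others. SAP 3.2.3 likewise gives estimation at least equal weight and promises the intervals whatever the test shows. That lowers the stakes. But SAP 3.2.3 also names the comparison as the primary analysis and SAP 3.7 assigns it alpha 0.05, so its stated power should be correct.

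Finally, the A/B lettering and the choice of enrolled patients rather than completers are separate, smaller matters. On completers, the 25-point comparison has 78.7% power, hardly different from the approximate 80% claimed. Neither point is needed for this conclusion.

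**Conclusion.** The concern holds. Under the SAP's own formula, with 58 and 38 patients, a mycophenolate rescue rate of 0.42 and two-sided alpha 0.05, power for a 17-point difference is about 43% against the stated 80%, an overstatement of some 37 points (80 − 43). The figure that does carry about 80% power is a 25-point difference, 0.42 versus 0.17. That 0.17 was transcribed as a difference is an inference, but a strong one, since the table row and the back-solved rate of 0.171 both point to it.

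The result rests only on inputs printed in the SAP and on the enrolled counts being reached. The error affects one sentence and does not touch the design, the sample size or the planned analysis. It should be corrected.

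**What to change.** In SAP 3.4.2, Specific Aim 2, change the sentence so that the difference with approximately 80% power is 25 percentage points (0.42 versus 0.17). It will then agree with the second row of the power table and with the closing summary. The cost is one corrected sentence.

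Two optional clarifications could be made at the same time:
- Use drug names in the power table, or the same A/B letters as the text.
- Say that the powers are computed on patients expected to enter rescue treatment, since the SAP notes that "the number enrolling does not include loss to follow-up". Neither the enrolled nor the completer count makes an explicit allowance for failures who never enter Phase II. Protocol 3.2.1 foresees refusals ("Patients who refuse to switch to Phase II should be encouraged to return for a 6-month visit"), Protocol 4.1.2 sets a two-week entry window, and Protocol 5.6 bars switching after a serious laboratory event. The SAP expects about 5% per drug to discontinue for safety, but the documents do not say what share of these would be barred, or how many patients would refuse or miss the window.

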5.6. Laboratory measurements

Hematology and serum chemistry will be monitored in all patients prior to enrollment and throughout participation in the study. Each of the participating sites has an accredited onsite laboratory where all blood draws and laboratory measurements will be performed. The following will be measured and recorded on the Laboratory Report Form (Section A.8) for each:

Hematology

- Hemoglobin and/or hematocrit
- Platelet count
- White blood cell count (WBC)
 - % neutrophils; % lymphocytes
 - CD4 lymphocyte count ([REDACTED] sites only, at Baseline, Month 3, 6, & 12)

Serum Chemistry

- SGOT (AST)
- SGPT (ALT)
- Creatinine
- Serum or urine pregnancy test

Laboratory measurements used for baseline visits should be collected 4 weeks prior to enrollment. Those used for follow-up visits may be collected at any time within the study visit window. Laboratory measurements must be collected at each study visit.

All abnormal values will be reported on the Adverse Event Checklist (Section A.10) and monitored for resolution on the Adverse Event Log. Abnormalities which result in a non-serious adverse event (i.e. AST or ALT increasing to twice the upper limit of normal) will result in immediate stopping of study medications. As these abnormalities are often reversible, patients will be allowed one month to regain eligibility. If the lab results have returned to normal within one month, patients may be re-administered the study drug according to protocol. Labs can be checked prior to one month, and if normal, treatment can resume. Otherwise, treatment failure will be declared and patients may be treated according to best medical judgment of physician. They should still be followed for their 6th months visit and be treated according to the best medical judgment of their physician.

Laboratory abnormalities which meet the designated threshold of a severe adverse event (SAE) will result in immediate stopping of study medications, and should be reported on the Serious Adverse Event Narrative form (Section A.12). Treatment failure will be declared, and patients will be treated according to the best medical judgment of their physician, but still follow-up for 6 months. If a lab SAE occurs, patients will not switch to Phase II.

6. Adverse events

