4. *Quality of life.* For a power calculation, we consider the SF-36 questionnaire, which has two scales, the MCS and the PCS. The raw score standard deviation will be assumed to be 8.4 points; we assume a correlation between baseline and six months of 0.6.^{16, 17} Assuming that the baseline score will “explain” roughly 36% of the variance allows us to assume a corrected raw score standard deviation of 6.72 in a simplified calculation in which we treat the analysis as a T-test. The same power calculation formula used in (3) above reveals that **our sample size provides approximately 80% power to detect a raw score difference of roughly 2.57 between the two treatment groups.** This difference is roughly comparable to the small difference in scores found between intermediate uveitis patients and the general population¹⁶, a difference we believe to be more than sufficient to detect clinically significant results. Note that the population mean of this score is standardized to 50 on 0 to 100 scale. Similar analyses will be conducted for the vision related quality of life (i.e. NEI-VFQ-25 and the IND-VFQ).

5. *Rate of discontinuation.* Based on retrospective studies, we expect approximately 13% to discontinue methotrexate due to tolerability and 5% to discontinue due to safety (laboratory abnormalities or other serious adverse events). We expect approximately 4% to discontinue mycophenolate mofetil due to tolerability and 5% to discontinue due to safety.^{12, 18-20} For the purpose of the power calculation, we assume 10% loss to follow-up and consider only the comparison of discontinuation due to tolerability. **We use the power formula given in Freedman et al (p. 104) to calculate a power of 61% for this comparison.**³

6. *Macular edema.* Previous studies suggest approximately 38% of individuals with uveitis will manifest macular edema.²¹ **We have approximately 80% power to detect a difference of a factor of two in the final proportion of macular edema (19% vs 38%).**

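### The Aim 2 power (87%, and 80% for a 25-point difference) uses enrolled rather than completing patients and counts safety failures, most of whom are not expected to switch; about 82–86% and 74–79% is supportable

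*Combined protocol and SAP*

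**What the plan says.** SAP 3.4.2, Specific Aim 2, defines the number available in each rescue group as the number randomized, times Aim 1 retention, times the Aim 1 failure fraction, times Aim 2 retention. Aim 2 retention is set at 0.95: "Finally, we are assuming an additional 5% loss to follow-up during Specific Aim 2". A small table then lists 58.3 and 38.9 patients expected to enter and 55.4 and 36.9 expected to complete.

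The next paragraph takes the entering numbers, rounded down to 58 and 38, into the power formula. The text reports: "These assumptions yield a power of 0.87 if the rate of success with methotrexate rescue is 0.15". The summary after the power table says that these numbers, "58 enrolled in Drug A, and 38 in Drug B) should provide approximately 80% power to detect a difference of 25% between the two groups", with "a two-tailed alpha of 0.05".

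On safety, item 5 of the Aim 1 secondary outcomes in the same section expects 5% of the methotrexate arm to discontinue for laboratory abnormalities or other serious adverse events. For the other arm it says: "We expect approximately 4% to discontinue mycophenolate mofetil due to tolerability and 5% to discontinue due to safety". SAP 3.2.2 scores discontinuation for adverse events as failure in the primary outcome. The protocol then limits who may switch:

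- Section 5.6, on laboratory measurements: "If a lab SAE occurs, patients will not switch to Phase II". Section 2.5.2 says the same of laboratory abnormalities that have not resolved after 28 days.
- Section 4.1.1 expects that most patients with a serious adverse event will not be allowed to switch, with some exceptions.
- Sections 2.5.2, 4.5.1 and 6.3 leave non-laboratory cases to the Medical Monitor, so selected safety failures may enter Phase II.

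**The concern.** The plan assumes a 5% loss during Aim 2, works out its effect on the numbers, and then leaves it out of the power. SAP 3.5 makes complete-case analysis primary. If that carries over to Aim 2, completers are the patients analysed.

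The plan also makes no deduction for safety failures. They are inside the 40% and 60% Aim 1 failure fractions, so they are inside the 58 and 38, yet by the protocol most of them would not receive the second drug.

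Both omissions push the stated power upwards. SAP 3.2.3 names this comparison as the Aim 2 primary analysis, and a reader facing a null result would use the stated power to interpret it.

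**Working it through.** **Inputs, all from SAP 3.4.2**

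- 108 randomized per arm and Aim 1 retention 0.90, so 108 × 0.90 = 97.2 retained per arm.
- Aim 1 success 0.40 and 0.60, so failures are 97.2 × 0.60 = 58.32 and 97.2 × 0.40 = 38.88.
- Aim 2 retention 0.95, so completers are 58.32 × 0.95 = 55.4 and 38.88 × 0.95 = 36.9.
- Success with mycophenolate rescue p1 = 0.42, paired with n1 (the larger group). Success with methotrexate rescue p0 = 0.15 or 0.17, paired with n0.
- Safety discontinuation 5% per arm, two-sided alpha 0.05.

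The sentence before the power table calls the second scenario a difference of 17%. The table and the summary show that 0.17 is the methotrexate rescue rate, and that the difference is 0.42 − 0.17 = 0.25.

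**Formula (the SAP's own)**

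Power = Φ( |p1 − p0| / √[p0(1 − p0)/n0 + p1(1 − p1)/n1] − 1.960 )

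**Step 1. Reproduce the stated figures with 58 and 38**

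- 0.42 vs 0.15: standard error 0.0869; 0.27/0.0869 = 3.106; 3.106 − 1.960 = 1.146; power 87.4% (stated 87%).
- 0.42 vs 0.17: standard error 0.0890; 0.25/0.0890 = 2.810; 2.810 − 1.960 = 0.850; power 80.2% (stated 80%).

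The stated power therefore rests on enrolled patients.

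**Step 2. Use the SAP's completers, 55.4 and 36.9**

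- 0.42 vs 0.15: standard error 0.0886; 3.048 − 1.960 = 1.088; power 86.2%.
- 0.42 vs 0.17: standard error 0.0907; 2.758 − 1.960 = 0.798; power 78.8%.

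**Step 3. Also remove safety failures who do not switch**

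Five per cent of 97.2 is 4.86 patients per arm. If a share f of them is barred, completers are (58.32 − 4.86f) × 0.95 and (38.88 − 4.86f) × 0.95. The documents do not give f, so it is varied.

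| Share barred, f | Completers | 0.42 vs 0.15 | 0.42 vs 0.17 |
|---|---|---|---|
| 0 | 55.4 / 36.9 | 86.2% | 78.8% |
| 0.5 | 53.1 / 34.6 | 84.4% | 76.6% |
| 0.75 | 51.9 / 33.5 | 83.4% | 75.5% |
| 1 | 50.8 / 32.3 | 82.3% | 74.3% |

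Taking the 5% from 108 instead of 97.2, with all barred, leaves 50.3 and 31.8 and gives 81.8% and 73.7%.

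**Step 4. Detectable difference at 80% power, starting from 0.42**

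- Enrolled (58/38): 24.9 points.
- Completers: 25.3 points.
- Completers with all safety failures removed: 26.4 points.

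**Step 5. The power table**

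The first six rows reproduce with the numbers printed in them. The seventh (58/38, 0.40 vs 0.15) does not: standard error 0.0866; 0.25/0.0866 = 2.888; 2.888 − 1.960 = 0.928; power 82.3%, against 80% stated.

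**The case against.** The strongest reply is that the demonstrable slip is small. Completers alone cost 1 to 2 points, the SAP calls its figures approximate, and the detectable difference moves only from 24.9 to 25.3 points. The main scenario stays above 80% throughout. The plan warns that Aim 2 numbers depend heavily on Aim 1, its table already varies the group sizes (40 per group gives 80% for 0.42 vs 0.15), and SAP 3.2.3 treats estimating the rescue success rates as arguably at least as important as the test. All of this stands, and it keeps the point minor. It does not remove the mismatch with the SAP's own definition of available patients. The 40/40 row also does not answer the safety question for the 25-point claim.

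Two stronger readings are tempting, and the documents support neither.

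- A reader might infer that 82% and 74% are simply the correct values. They require every safety failure to be barred. Only laboratory cases are excluded outright; the Medical Monitor may let selected others switch, the SAP keeps safety as a reason-for-failure category in its Aim 2 analyses, and the 5% is not divided between the two kinds.
- A reader might infer from the seventh row that the table mixes enrolled and completing numbers. The SAP's completers give 80.9% for that row, and only truncation to 55 and 36 gives 80.3%. Coarse rounding or an isolated slip would explain it equally well.

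**Conclusion.** The point holds as a modest overstatement of power. The supportable ranges are about 82–86% for 0.42 vs 0.15 (stated 87%) and about 74–79% for the 25-point difference (stated 80%). The upper ends use completers only. The lower ends assume that all of the expected safety failures are barred. Because the protocol expects most patients with a serious adverse event not to switch, the lower half of each range is the more likely. Most of any drop to the lower end comes from the safety exclusion rather than from the Aim 2 dropout.

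The result rests on the SAP's own success rates and formula, on 5% of the retained patients per arm stopping for safety, and on 0.95 retention applied after the safety exclusion. The seventh table row is wrong on its printed inputs; the cause is not known.

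**What to change.** In SAP 3.4.2, Specific Aim 2:

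1. Recompute the text, the power table and the summary sentence with expected completers who can switch, using that one definition throughout.
2. State the assumed share of safety failures who do not enter Phase II, say that it is an assumption, and report the range: about 82–86% for 0.42 vs 0.15 and 74–79% for 0.42 vs 0.17.
3. Correct the 0.40 vs 0.15 row. If 58 and 38 are kept there, the figure is 82%.

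The cost is a revised paragraph and table, with slightly less favourable power. Sample size, eligibility for Phase II and the analysis do not change.
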